7.1.4 Methods for Handling Missing Data

All available efficacy and safety data will be included in data listing and tabulations. No imputation of values for missing data will be performed unless otherwise specified.

- For UFS-QoL and WPAI, published scoring manuals and guidelines will be used to calculate UFS-QoL and WPAI scale scores and handle missing data (see Appendix 3 and 4, respectively).
- For myoma or uterus volume, if D1 and D2 of the myoma or uterus are present but D3 is missing, then the volume will be calculated as $D1*D2*D2*\pi/6$ (cm^3).
- For LH, FSH, E₂, P and clinical laboratory tests, values less than the lower limit of quantification will be treated as zero when calculating the descriptive statistics.
- Disease duration with first diagnosis date of uterine fibroid that are completely or partially missing will be derived as follows:
 1. If the year is missing, then the disease duration will be treated as missing.
 2. If the year is present but the month is missing, then the month will be treated as January for the calculation.

7.2 Analysis Sets

Refer to the Handling Rules for Analysis Data.

7.3 Disposition of Subjects

7.3.1 Study Information

Analysis Set: All Subjects Who Signed the Informed Consent Form

Analysis

Variable(s) : Date first subject signed informed consent form
Date of last subject's last visit/contact
MedDRA version
WHO Drug version
SAS version used for creating the datasets

Analytical

Method(s) : (1) Study Information

Study information shown in the analysis variables section will be provided.

7.3.2 Screen Failures

Analysis Set: All Subjects Who Were Not Randomized

Analysis

Variable(s) : Age (years) [20<= - <30, 30<= - <40, 40<= - <50, 50<= - <=Max]

Analytical

Method(s) : (1) Screen Failures

Frequency distributions for categorical variables and descriptive statistics for continuous variables will be provided.

7.3.3 Subject Eligibility

Analysis Set: All Subjects Who Signed the Informed Consent Form

Analysis

Variable(s) : Eligibility status [Eligible for Randomization, Not Eligible for Randomization]

Primary Reason for Subject Not Being Eligible [Death, Adverse Event, Screen Failure, Protocol Deviation, Lost to Follow-up, Withdrawal by Subject, Study Terminated by Sponsor, Pregnancy, Other]

Analytical

Method(s) : (1) Eligibility for Randomization

Frequency distributions will be provided. When calculating percentages for the primary reasons for subject not being eligible, the total number of ineligible subjects will be used as the denominator.

7.3.4 Number of Subjects Randomized by Site and Treatment Group

Analysis Set: Randomized Set

CONFIDENTIAL

Analysis

Variable(s) : Randomization status [Randomized]
Stratum: Site [Site numbers will be used as categories]

Analytical

Method(s) : (1) Number of Subjects Randomized by Site and Treatment Group
Frequency distribution will be provided for each stratum by treatment group and overall.

7.3.5 Disposition of Subjects

Analysis Set: Randomized Set

Analysis Double-blind study drug

Variable(s) : administration status [Randomized but Not Treated]
Reason for not being treated [Death, Adverse Event, Protocol Deviation, Lost to Follow-up, Withdrawal by Subject, Study Terminated by Sponsor, Pregnancy, Lack of Efficacy, Bone Mineral Density Loss, Recovery Leading to Surgery, Reduction of HGB Concentration, Other]
Double-Blind Study Drug [Completed Study Drug, Prematurely Discontinued Study Drug]
Completion Status

Reason for Discontinuation of Study Drug [Death, Adverse Event, Protocol Deviation, Lost to Follow-up, Withdrawal by Subject, Study Terminated by Sponsor, Pregnancy, Lack of Efficacy, Bone Mineral Density Loss, Recovery Leading to Surgery, Reduction of HGB Concentration, Other]

Completion Status of the Follow- [Completed Follow-up Period,

up Period	Prematurely Discontinued Follow-up Period]
Reason for Discontinuation of the Follow-up Period	[Death, Adverse Event, Protocol Deviation, Lost to Follow-up, Withdrawal by Subject, Study Terminated by Sponsor, Pregnancy, Lack of Efficacy, Bone Mineral Density Loss, Recovery Leading to Surgery, Reduction of HGB Concentration, Other]
Analytical	
Method(s) :	(1) Disposition of Subjects
	Frequency distributions will be provided for each treatment group and overall. When calculating percentages for the reasons for not being treated, the total number of subjects not treated by the study drug will be used as the denominator. When calculating percentages for the reasons for discontinuation, the total number of subjects who prematurely discontinued will be used as the denominator.

7.3.6 Protocol Deviations

Analysis Set: Randomized Set

Analysis

Variable(s) :	Protocol Deviation	[Major GCP Violations, Deviations of Protocol Entry Criteria, Deviations of Discontinuation Criteria, Deviations Related to Treatment Procedure or Dose, Deviations Concerning Excluded Medication or Therapy, Deviations to Avoid Emergency Risk]
Analytical		

Method(s) :

(1) Protocol Deviations
Frequency distribution will be provided by treatment group and overall for each deviation category. A subject who has several deviations will be counted once in each appropriate category. A subject who has several

deviations that can be classified into the same category will be counted only once.

7.3.7 Analysis Sets

Analysis Set: Randomized Set

Analysis

Variable(s) : Handling of Subjects and Subject Data [Categories are based on the specifications in Handling Rules for Analysis Data]

Analysis Sets

Full Analysis Set	[Included]
Per Protocol Set	[Included]
Safety Analysis Set	[Included]

Analytical

Method(s) : (1) Subjects Excluded from Analysis Sets
(2) Subject Data Excluded from Analysis Sets
(3) Analysis Sets

Frequency distributions will be provided by treatment group for (1) and (2), and by treatment group and overall for (3). For (1) and (2), a subject who has several reasons for exclusion will be counted once in each appropriate category. A subject who has several reasons for exclusion that can be classified into the same category will be counted only once.

7.4 Demographic and Other Baseline Characteristics

Analysis Set: Randomized Set

Analysis

Variable(s) : Age (years) [20<= - <30, 30<= - <40, 40<= - <50, 50<= - <Max]
Height (cm) [Min<= - <150, 150<= - <160, 160<= - <170, 170<= - <Max]
Weight (kg) at Baseline [Min<= - <50, 50<= - <60, 60<= - <70, 70<= - <80,

BMI (kg/m ²) at Baseline	80<= - <=Max] [Min<= - <18.5, 18.5<= - <25.0, 25.0<= - <=Max]
Smoking Classification	[The subject has never smoked, The subject is a current smoker, The subject is an ex-smoker]
Birth Experience	[Yes, No]
Disease Duration (years)	[Min<= - <=1, 1< - <=3, 3< - <=5, 5< - <=10, 10< - <=Max]
Type of Uterine Fibroid	
Subserosal Fibroid	[Yes, No]
Intramural Fibroid	[Yes, No]
Submucosal Fibroid	[Yes, No]
Cervical Fibroid	[Yes, No]
Stopped Any Medications for Uterine Fibroids	[Yes, No]
Type of Medication for Uterine Fibroid	
GnRH Agonist	[Yes]
Herbal Medicine	[Yes]
Other Medicines for Uterine Fibroids	[Yes]
Any Surgery for Uterine Fibroids	[Yes, No]
Volume of Myoma at Baseline (cm ³)	[Min<= - <=28, 28< - <=170, 170< - <=700, 700< - <=Max]
Volume of Uterus at Baseline (cm ³)	[Min<= - <=28, 28< - <=170, 170< - <=700, 700< - <=Max]
PBAC Score at Baseline	[120<= - <200, 200<= - <500, 500<= - <=Max]
NRS Score at Baseline	[Min<= - <4, 4<= - <7, 7<= - <=Max]
UFS-QOL Score at Baseline	
Symptom Severity	[Min<= - <=25, 25< - <=50, 50< - <=75, 75< - <=Max]
Concern	[Min<= - <=25, 25< - <=50, 50< - <=75, 75< - <=Max]
Activities	[Min<= - <=25, 25< - <=50, 50< - <=75, 75< - <=Max]

Energy/Mood	[Min<= - <=25, 25< - <=50, 50< - <=75, 75< - <=Max]
Control	[Min<= - <=25, 25< - <=50, 50< - <=75, 75< - <=Max]
Self-consciousness	[Min<= - <=25, 25< - <=50, 50< - <=75, 75< - <=Max]
Sexual Function	[Min<= - <=25, 25< - <=50, 50< - <=75, 75< - <=Max]
HRQL Total	[Min<= - <=25, 25< - <=50, 50< - <=75, 75< - <=Max]
HGB at Baseline (g/dL)	[Min<= - <10, 10<= - <12, 12<= - <=Max]
HCT at Baseline (%)	
Serum Fe at Baseline (µg/dL)	
Serum Ferritin at Baseline (ng/mL)	
Dosage of leuprorelin vial	[1.88 mg, 3.75 mg]

Analytical

Method(s) : (1) Summary of Demographics and Baseline Characteristics
Frequency distributions for categorical variables and descriptive statistics for continuous variables will be provided by treatment group and overall.

7.5 Medical History and Concurrent Medical Conditions

Analysis Set: Safety Analysis Set

Analysis

Variable(s) : Medical History
Concurrent Medical Conditions

Analytical

Method(s) : (1) Medical History by System Organ Class and Preferred Term
(2) Concurrent Medical Conditions by System Organ Class and Preferred Term

Frequency distributions will be provided for each treatment group. MedDRA dictionary will be used for coding. Summaries will be provided using SOC and PT, where SOC will be sorted alphabetically and PT will be sorted in decreasing frequency.

A subject with multiple occurrences of medical history or concurrent medical condition within a SOC will be counted only once in that SOC.
A subject with multiple occurrences of medical history or concurrent medical condition within a PT will be counted only once in that PT.

7.6 Medication History and Concomitant Medications

Analysis Set: Safety Analysis Set

Analysis

Variable(s) : Medication History
Concomitant Medications

Analytical

Method(s) : (1) Medication History by Preferred Medication Name
(2) Concomitant Medications That Started Prior to and Were Ongoing at Baseline as well as Those That Started After Baseline by Preferred Medication Name

Frequency distributions will be provided for each treatment group. WHO Drug dictionary will be used for coding. Summaries will be provided using preferred medication names and sorted in decreasing frequency based on the number of reports. A subject who has been administered several medications with the same preferred medication name will be counted only once for that preferred medication name.

7.7 Study Drug Exposure and Compliance

Analysis Set: Safety Analysis Set

Analysis Duration of Exposure to Double- [1<= - <=14, 15<= - <=42,

Variable(s) : Blind Study Drug (days) 43<= - <=84, 85<= - <=168
169<= - <=Max]

Double-Blind Study Drug [Min<= - <80, 80<= - <90, 90<= - <=Max]

Compliance (%)

Maximum Drug Holidays (days) [0, 1<= - <4, 4<= - <=Max]

Exposure to Double-Blind

leuprolerlin vial (times)

Analytical

Method(s) : (1) Study Drug Exposure and Compliance

Frequency distributions for categorical variables and descriptive statistics for continuous variables will be provided by treatment group and overall.

7.8 Efficacy Analysis

7.8.1 Primary Efficacy Endpoint(s)

7.8.1.1 Primary Analysis

Analysis Set: Full Analysis Set

Analysis

Variable(s): Proportion of subjects with a total PBAC score of < 10 from Week 6 to 12

Analytical Method(s): The point estimate and 2-sided 95% confidence interval of the proportion of subjects with a total PBAC score of < 10 from Week 6 to 12 will be summarized by treatment group. The point estimate and 2-sided 95% confidence interval of the difference in the percentage will be calculated between TAK-385 40 mg group and leuprorelin group (TAK-385 40 mg group – leuprorelin group), using Farrington and Manning (FM) method. In addition, non-inferiority test using FM method with a non-inferiority margin of 15% will be conducted for the comparison between TAK-385 40 mg group and leuprorelin group. If the lower bound of the 95%CI is greater or equal to the non-inferiority margin of -15%, then non-inferiority of TAK-385 40mg to leuprorelin will be concluded.

7.8.1.2 Secondary Analysis

Analysis Set: Per Protocol Set

Analysis

Variable(s): Proportion of subjects with a total PBAC score of < 10 from Week 6 to 12

Analytical

Method(s): An analysis similar to the above “Primary analysis” will be performed

using the PPS to assess the robustness of the results.

7.8.1.3 Adjustments for Covariates

Analysis Set: Full Analysis Set

Analysis

Variable(s): Proportion of subjects with a total PBAC score of < 10 from Week 6 to 12

Covariate(s): PBAC Score at Baseline [120<= - <200, 200<= - <500, 500<= - <=Max]

Analytical

Method(s): The difference between groups in the proportion of subjects with a total PBAC score of < 10 from Week 6 to 12 will be analyzed using binomial regression with the identity link that includes treatment group and PBAC score at baseline as independent categorical variable.

7.8.1.4 Examination of Subgroups

Analysis Set: Full Analysis Set

Analysis

Variable(s): Proportion of subjects with a total PBAC score of < 10 from Week 6 to 12

Subgroup(s): Age (years) [20<= - <30, 30<= - <40, 40<= - <50, 50<= - <=Max]

BMI (kg/m^2) at Baseline [Min<= - <18.5, 18.5<= - <25.0, 25.0<= - <=Max]

PBAC Score at Baseline [120<= - <200, 200<= - <500, 500<= - <=Max]

Birth Experience [Yes, No]

Volume of Uterus at Baseline (cm^3) [Min<= - <=28, 28< - <=170, 170< - <=700, 700< - <=Max]

Type of Uterine Fibroid Subserosal Fibroid [Yes, No]

Intramural Fibroid [Yes, No]

Submucosal Fibroid [Yes, No]

Analytical

Method(s): (1) Descriptive Statistics

The point estimate and 2-sided 95% confidence interval of the proportion of subjects with a total PBAC score of < 10 from Week 6 to 12 will be summarized for above each subgroup by treatment group.

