6.1.2 Dose Level and Regimen

At VISIT 3, subjects will be randomized in a 1:1 ratio to either the TAK-385 40 mg group or leuprorelin group. Study drug (TAK-385 40 mg + leuprorelin placebo or TAK-385 placebo + leuprorelin) will be administered in a double-dummy method from the day of VISIT 3 to the day before VISIT 10 (or until early termination) under double-blind conditions.

The investigator or subinvestigator will decide the dosage of leuprorelin at VISIT 2 in accordance with the approved dosage and administration, considering the body weight and symptoms of the individual subject. Leuprorelin (or leuprorelin placebo) should be administered SC (injection) once every 4 weeks using the same dose throughout the Run-in and Treatment.

TAK-385 (or TAK-385 placebo) will be administered daily as a single oral dose before breakfast.

[figure not shown]

Figure 6.a Schematic of Study Design

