8.1.3 Dose and Regimen

[Table 8.a](#) describes the dose and tablet count that will be provided to each group.

Table 8.a Dose and Regimen

Period	Group	Dose and Regimen
Run-in	All group	
• One TAK-385 placebo tablet per day• One leuprorelin acetate (1.88 mg or 3.75 mg) placebo injection once/4 weeks
Treatment	TAK-385 40 mg group	
• One TAK-385 40 mg tablet per day• One leuprorelin acetate (1.88 mg or 3.75 mg) placebo injection once/4 weeks
	Leuprorelin group	
• One TAK-385 placebo tablet per day• One leuprorelin acetate (1.88 mg or 3.75 mg) injection once/4 weeks

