8.3 Randomization Code Creation and Storage

The supervisor on randomization personnel generates a randomization schedule. All randomization information will be stored in a secured area, accessible only by authorized personnel.

At VISIT 3, subjects will be randomized in a 1:1 ratio to either the TAK-385 40 mg group or leuprorelin group.

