7.0 METHODS OF ANALYSIS AND PRESENTATION

7.1 General Principles

All statistical analyses will be conducted using SAS® Version 9.2, or higher.

A statistical test for the primary endpoint will be reported as 1-sided and will be assessed at $\alpha=0.025$ significance level and all confidence intervals will be reported as 2-sided unless otherwise stated. P-values will be rounded to 4 decimal places prior to assessment of statistical significance.

Means and medians will be presented to 1 more decimal place than the recorded data. The standard deviations (SDs) will be presented to 2 more decimal places than the recorded data. Confidence intervals about a parameter estimate will be presented using the same number of decimal places as the parameter estimate.

Where appropriate, variables will be summarized descriptively by study visit. For the categorical variables, the count and proportions of each possible value will be tabulated by treatment group. The denominator for the proportion will be based on the number of subjects who provided non-missing responses to the categorical variable. For continuous variables, the number of subjects with non-missing values, mean, median, SD, minimum, and maximum values will be tabulated. Confidence intervals for continuous variables will be calculated based on t-statistics and ones for categorical variables will be based on Wald confidence intervals without using any model, unless otherwise stated.

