7.8.2 Secondary Efficacy Endpoint(s)

7.8.2.1 PBAC Score

Analysis Set: Full Analysis Set

Analysis

Variable(s): Proportion of subjects with a total PBAC score of < 10 from Week 2 to 6
Proportion of subjects with a total PBAC score of < 10 from Week 18 to 24
Proportion of subjects with a total PBAC score of < 10 for 6 weeks before the final dose of study drug

Analytical

Method(s): For each variable, frequency will be summarized by treatment group. The point estimate and 2-sided 95% confidence interval of the difference in the percentage will be calculated between TAK-385 40 mg group and leuprorelin group, using FM method with the non-inferiority margin of -15%. The confidence interval will be presented in a descriptive manner and not for the purpose of statistical inference.

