7.8.2.3 Hemoglobin

Analysis Set: Full Analysis Set

Analysis

Variable(s): HGB (g/dL) [Min<= - <12, 12<= - <=Max]

Change from baseline on HGB [Min<= - <1, 1<= - <=Max]
(g/dL)

Subgroup(s): Oral iron preparation use at [Yes, No]
baseline

HGB at Baseline (g/dL) [Min<= - <12, 12<= - <=Max]

Visit: Baseline, Week 4, 8, 12, 16, 20, 24 and Follow-up

Analytical

Method(s): Summary statistics will be provided for the observed values and the changes from baseline by treatment group for each visit.

The mean differences in the change from baseline between TAK-385 40 mg and leuprorelin groups and the two-sided 95% confidence intervals will be provided for each visit.

For categorical variables, frequency will be summarized by treatment group for each visit. The differences in the percentage between TAK-385 40 mg and leuprorelin groups and the two-sided 95% confidence intervals will be provided for each visit.

Additionally, the above mentioned analysis will also be conducted for each subgroup.

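### Should the subgroup display of the primary endpoint be split by leuprorelin dose and show the between-arm difference?

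*SAP*

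**What the plan says.** **Subgroup display.** SAP 7.8.1.4 lists age, BMI, baseline PBAC score, birth experience, uterine volume and three fibroid types. For each level, the responder proportion and its 95% CI "will be summarized for above each subgroup by treatment group". No difference between arms is named, and leuprorelin dose is not listed.

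**Differences elsewhere.** SAP 7.8.1.1 calculates the primary difference "using Farrington and Manning (FM) method". SAP 7.8.2.1 does so for the other PBAC periods, "using FM method with the non-inferiority margin of -15%. The confidence interval will be presented in a descriptive manner". For hemoglobin, SAP 7.8.2.3 plans between-arm differences with CIs and then says: "Additionally, the above mentioned analysis will also be conducted for each subgroup". Where no method is named, SAP 7.1 says that "ones for categorical variables will be based on Wald confidence intervals without using any model".

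**Leuprorelin dose.** Under Protocol 6.1.2 the investigator will "decide the dosage of leuprorelin at VISIT 2 in accordance with the approved dosage and administration, considering the body weight and symptoms". Randomisation comes later. Protocol 8.3 says: "At VISIT 3, subjects will be randomized in a 1:1 ratio to either the TAK-385 40 mg group or leuprorelin group", and no stratification factor is stated. In Protocol Table 8.a the TAK-385 group receives "One leuprorelin acetate (1.88 mg or 3.75 mg) placebo injection once/4 weeks", so every woman has a dose label whichever arm she joins. SAP 7.4 tabulates that dose as a baseline characteristic. No efficacy analysis in the SAP uses it.

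**The concern.** The trial tests a difference, but the subgroup table shows two separate proportions. A reader checking consistency gets no planned interval for the quantity of interest. Hemoglobin, a secondary endpoint, gets that interval by subgroup.

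The comparator is also given at two doses. The leuprorelin response figures cited for the sample size (Protocol 13.3, SAP 6.0) come from a 3.75 mg group, while the label quoted in Protocol 6.2.2 gives 1.88 mg as the usual dose. The documents give no response figure for 1.88 mg. A regulator or reader may ask whether the result looks alike at the two doses, and no planned output answers directly.

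Dose would be a clean subgroup to use. It is set before randomisation and exists in both arms, so within a dose TAK-385 against leuprorelin is still a randomised comparison. The data are already collected. What would be at stake is the description of the result, not the decision on non-inferiority.

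**Working it through.** **Inputs.** Response 83.6% in both arms, margin 15 points, one-sided 0.025, 129 evaluable per arm, 144 randomised per arm (Protocol 13.3, SAP 6.0). The dose split is not in the documents. I assume 50/50, 80/20 and 90/10.

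**1. The plan's own figure.** n = 2 × 0.836 × 0.164 × (1.960 + 1.282)² / 0.15² = 128.1, rounded up to 129 per arm, with power 90.2%. Then 129 / 0.90 = 143.3, rounded up to 144. Both figures reproduce, and neither depends on dose.

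**2. Width of a within-dose difference.** The Farrington-Manning (FM) half-width is 1.96 × √[q₁(1−q₁)/n₁ + q₂(1−q₂)/n₂], where q₁ and q₂ are the restricted estimates under q₁ − q₂ = −0.15. With equal arms and 83.6% observed in both, q₁ = 0.737 and q₂ = 0.887. The half-width is then 1.96 × √(0.2939/n), or about 106.3/√n points.

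| Evaluable per arm | Where it arises | Half-width (points) |
|---|---|---|
| 129 | whole trial | 9.4 |
| 116 | larger stratum, 90/10 | 9.9 |
| 103 | larger stratum, 80/20 | 10.5 |
| 64 | each stratum, 50/50 | 13.3 |
| 26 | smaller stratum, 80/20 | 20.8 |
| 13 | smaller stratum, 90/10 | 29.5 |

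The Wald variance gives slightly smaller values (12.8, 20.2 and 28.6 points for shares of 50%, 20% and 10%) and the same picture.

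**3. Consistency between doses.** The half-width for the difference of the two dose-specific differences is the root of the summed squares:
- 50/50 (64 and 65 per arm): √(13.28² + 13.18²) = 18.7 points
- 80/20: √(10.47² + 20.84²) = 23.3 points
- 90/10: √(9.87² + 29.47²) = 31.1 points

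Each exceeds the 15-point margin.

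**4. Chance that a dose stratum clears the margin when the arms are truly equal.** Exact binomial probability that the FM lower bound is at or above −15%: 61% with 64 per arm, 30% with 26, 17% with 13, against about 90% with 129. A stratum that fails to clear it would be unsurprising and would say little about dose.

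**5. Chance imbalance.** With no stated stratification by dose, arms within a dose need not be equal. For a 26-subject stratum among 258 evaluable, the hypergeometric 95% range is 8/18 to 18/8. If an interval were shown only with at least 10 per arm, it would be missing with probability about 15%, and the widest one shown (10 TAK-385, 16 leuprorelin) would be about ±32 points.

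**6. What the existing table yields.** The listed subgroups have 4 + 3 + 3 + 2 + 4 + 2 + 2 + 2 = 22 levels. SAP 7.1 tabulates counts and proportions for categorical variables, so for each level a reader can subtract the two arms and can work out an interval. By dose, that is not possible from the planned output.

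**The case for a change.** The strongest case for a change is that it costs little and has precedent. It needs two rows and one column, uses no new data, and could copy the descriptive wording of SAP 7.8.2.1. SAP 7.8.2.3 already shows differences by subgroup for hemoglobin. The SAP's change table records subgroups removed and added after blind review, so an edit of this kind would be routine. Fixing the split before unblinding would also avoid a post hoc one.

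The listed subgroups replace dose only in part. The label's reasons for 3.75 mg are weight and uterine size, which BMI and uterine volume approximate, but the investigator also weighs symptoms and neither variable identifies the vial used.

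All of that stands as an argument for a useful option. It does not show that the plan is wrong. Protocol 13.1.3 asks for no subgroup analysis of the primary endpoint, so SAP 7.8.1.4 already goes beyond it. The objectives name a single comparator given at either dose under its label, and the pooled contrast answers that question. Planning subgroup differences for hemoglobin does not make a per-arm display elsewhere defective. Dose rows set beside a −15% margin would also invite readers to judge non-inferiority dose by dose, which step 4 shows the data cannot support. Comparing the two doses with each other would further reflect weight, uterine size and symptoms.

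**Conclusion.** The description of the plan is accurate: dose is absent from the subgroup list and the table gives per-arm estimates only. It is a fair choice of display. Followed as written, the plan gives a sound answer to its stated objective, with no effect on the primary test, alpha or the 144 per arm.

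A dose split would give within-dose half-widths of roughly 10 to 30 points and between-dose half-widths of 18.7 to 31.1 points. It could describe the data but could establish neither consistency nor non-inferiority at each dose. These widths rest on 83.6% response in both arms, 129 evaluable per arm, equal arms within dose, and assumed splits between 50/50 and 90/10. A more extreme split would make the smaller stratum less informative still. A sponsor who wants the dose rows can add them as a labelled descriptive output, but the plan does not need them.
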